5.3 Screen Failures

A patient who has signed a consent form, has been assigned a screening number, but is not randomised is classified as a screen failure. Patient number, demography and reason for screen failure will be collected.

6 Study Treatments

6.1 Method for Assigning Eligible Patients to Treatment

Eligible patients will be assigned to one of the following three treatment groups, based on the randomisation schedule:

- Group 1: SC only (multilayer, multicomponent compression intended for the treatment of VLU)
- Group 2: 12 hours daily treatment with geko™ (XW, W-3 or variant) plus SC (multilayer, multicomponent compression intended for the treatment of VLU)

6.2 Description of the Investigational Device

The geko™ device is CE marked (GB12/87339; SGS, United Kingdom Ltd). The geko™ device is made from mylar (polyethylene terephthalate (PET)), it is enclosed in a polypropylene casing and a hydrogel layer will stick it to the skin. In this study the XW, W-3 or variant will be used. (Refer to Appendix 1. for Fitting Instructions).

6.3 Participant Investigational Device Use

Each geko™ device can be used only twice. Participants randomised to the geko™ 12 hour daily treatment groups will at each visit be provided with a sufficient number of geko™ devices to last until the next scheduled Treatment Phase visit. Participants should ensure that they always have enough devices to carry them through to the next scheduled Treatment Phase visit. Participants randomised to either geko™ group will be provided with a diary card on which their geko™ usage will be recorded. The participants should bring the diary card with them at each site visit at which the cards will be verified and signed.

6.4 Labelling

The study supplies will be labelled in accordance with all applicable regulatory requirements. Each investigator will be supplied with sufficient supplies to conduct the study.

Each geko™ device will have a number which will be unique to the particular device. The unique device number will be recorded in the participant diary each time it is used to provide a check that the allocated treatment has been provided. At each study visit the study device usage will be assessed and new devices provided.

6.5 Device Storage, Handling, Application and Disposition

The investigational devices will be supplied in single use labelled packages.

The whole device with the battery in place can be disposed of in domestic waste.

Details on application of the geko™ device and Instructions for Use are available in Appendix 1.

6.6 Product accountability

The Investigator or designee will verify the contents of each shipment against the shipping documents. Verification of investigational device receipt will be documented according to Sponsor's requirements.

An accountability log will be provided to the site for use by the Investigator to maintain current and accurate inventory records (batch, expiry, and quantity) covering the dispensing and the destruction of the investigational product.

At the conclusion of the study the Investigator must agree to return all investigational products as instructed by Sponsor.

6.7 Participant Training and Instructions

Participants randomised to either geko™ group will be trained in the use of the geko™ device and be provided with Instructions for Use. Such participants will also be instructed to hand in the above mentioned diary card at each study visit for verification and signature by the Investigator.

All participants will be instructed to ring or visit the study site if there is any issue with the compression bandaging such as, but not limited to, pain, discomfort, and removal or soiling of the bandage.

All participants will be instructed to contact the Investigator if signs or symptoms of infection develop prior to their next scheduled visit.

7 Concomitant Medications

All medications and therapies administered or taken by the participant throughout the study will be recorded in the source documents and on the appropriate page of the Case Report Form (CRF).

For each medication the following will be documented:

- Medication/treatment name (generic name may be used if trade name is unknown)
- Dose, unit, and frequency of dosing (individual dosages, not total daily dose). Note: Each new dose of medication should be recorded as a separate entry, with the exception of medications that are given on a sliding scale. For these, it is acceptable to enter the range of the dosage, including the start and stop dates for which the specified dosage range was used.
- Route of dosing
- Indication for use
- The start date
- The stop date (if applicable)

8. Excluded Therapies

The following treatments are prohibited throughout the study:

- Any neuro-modulation device
- Any other investigational treatment/medications

9 Description of Protocol Procedures and Assessments

9.1 Informed Consent

The Investigator or suitably qualified designee will obtain written informed consent for this study from all participants before the performance of any protocol-specific procedure.

In obtaining and documenting informed consent the Investigator must comply with applicable regulatory requirements and must adhere to Good Clinical Practice (GCP). The Investigator, or designee, must fully inform patients of all pertinent aspects of the study. Before written informed consent may be obtained, the Investigator, or a person designated by the Investigator, must provide the patient ample time and opportunity to inquire about details of the study and to decide whether or not to participate in the study. All questions about the study must be answered to the satisfaction of the patient. Prior to the patient taking part in the study, the written informed consent must be signed and personally dated by the patient and by the person who conducted the informed consent discussion.

The signed informed consent must remain in the patient's files and be available for verification by the study monitor. The patient's medical record should clearly indicate that the patient is participating in this study.

9.2 Assessment of Eligibility

At the RV1 and TV1, the Investigator must assess a patient's continued suitability and eligibility for the study, especially with regards to the Inclusion and Exclusion criteria of this Protocol described in Sections 3.1.2 and 3.1.3. If a patient is not suitable or eligible for the study then the patient will be a screen failure.

9.2.1 Re-Screening

If a patient fails to meet inclusion/exclusion criteria and is later reconsidered for participation, the patient will be re-consented and assigned a new screening number at the time of re-screening. Patients who fail their first screening attempt may be re-screened once again (i.e., up to two screenings per patient) and may be enrolled if they are found to meet all inclusion and no exclusion criteria at the screening visit.

9.3 Demographics, Medical History, Study Ulcer History

9.3.1 Demographics

For the purposes of this study, demographic information will include:

- Dates of Informed Consent Form signature
- Date of birth
- Gender

- Use of tobacco products

9.3.2 Medical History

A medical history will be recorded at RV1 and will include:

- All ongoing medical conditions
- All previously resolved medical conditions related to Venous Insufficiency or Leg Ulceration or which are relevant in the opinion of the Investigator

Medical histories will be recorded using the body system categories outlined below:

• Cardiovascular• Respiratory• Gastrointestinal• Renal• Hepatic• Neurological• Endocrine	
• Lymphatic• Hematologic• Immunologic• Dermatologic• Psychiatric• Genitourinary• Other
--	--

For each relevant history, the following will be documented:

- Disease/disorder/condition
- Year of diagnosis
- History status (resolved or ongoing)

9.3.3 Study Ulcer History

- Duration of the current study ulcer

Note: 'Duration' is defined as the length of time that the study ulcer has been open at this location (since the last time it was fully closed if the ulcer in question is a recurrent ulcer).

- Current compression bandaging system used for the study ulcer and length of time that this has been used
- Prior treatments that have been used on the study ulcer
- Age when the participant developed his/her first ulcer
- Total number of previous ulcers
- Location of the current study ulcer

Note: 'Study ulcer location' is defined by the ulcer being on the left or right leg, by the location of the ulcer on the malleolus, low gaiter or high calf, and by the positioning of the ulcer as lateral, medial, anterior or posterior.

- Number of additional leg ulcers and location of each present at the screening visits
- History of VLU recurrence

Note: 'Recurrence' is defined as the re-opening of an ulcer after healing.

- History of a DVT (deep vein thrombosis) in the study leg

9.4 Quality of Life Assessment Questionnaire (CWIS and EQ-5D-5L)

The Cardiff Wound Impact Schedule, CWIS, will be used to assess the "disease specific" QoL. A generic QoL questionnaire, the EQ-5D-5L questionnaire, will be used to assess the effects of treatments on the participants' QoL. Results may be used to derive a patient-reported outcome useful for health-related QoL claims on the investigational device treatment.

The questionnaires (and instructions for completing them) will be provided to all participants at the first Run-in Phase visit (RV1) and at TV1 prior to the application of randomised treatment. The questionnaires will also be provided and collected upon EOT, as part of the End of Study procedures.

The QoL assessments will be performed prior to any other study procedures, when scheduled, to minimise bias.

9.5 Physical Exam & Vital Signs

9.5.1 Physical Examination

The physical examination will be performed at study entry (RV1) and will include routine examinations for the following:

- Abnormalities of the extremities
- Neurologic abnormalities
- Heart/cardiovascular abnormalities
- Musculoskeletal abnormalities
- Dermatologic abnormalities
- Any other body system for which an abnormality is noted and which, in the opinion of the Investigator, is relevant to the safety of the participant or could impact safety or efficacy results for the participant; i.e. the abnormality is clinically significant.

Each abnormality will be recorded and the Investigator will record an assessment of its clinical significance.

9.5.2 Vital Signs

The following vital signs will be collected at study entry (RV1):

- Height

- Weight
- BMI (derived from the height and weight measurements)

9.6 Ankle-Brachial Pressure Index (ABPI)

Ankle Brachial Pressure Index (ABPI) is the ratio of blood pressure measured at the ankle to that measured at the arm. An ABPI < 0.8 indicates that there is a high probability that arterial insufficiency is present (positive predictive value 95% and negative predictive value 99%) in a general practice population). Compression therapy may be safely applied to patients with an ABPI >0.8 in addition to a comprehensive medical history.

If upon clinical examination the patient exhibits signs or symptoms that could suggest peripheral arterial disease, further investigations to determine vascular status may be warranted.

ABPI must be completed prior to any other study related procedures at the first Run-in Phase visit (RV1) unless a valid ABPI measurement has been taken within 8 weeks of the RV1 taking place.

9.7 Pain Assessment Using Visual Analogue Scale (VAS)

Pain intensity of the VLU is to be assessed before any dressing changes or other wound manipulations at all study visits (Run-in Phase and Treatment Phase).

The Visual Analogue Scale (VAS) is a commonly used pain assessment tool suitable for the purpose of this study. Participants will be using the VAS instrument to record study ulcer pain. They will be asked to mark the point that best represented the pain intensity at the ulcer site on a horizontal line (100mm in length) anchored by word descriptors at each end, as "no pain" on the left side and "worst pain possible" on the right side of the line. Importantly, the participant marks on the line or by pointing to a position on the line the point that he/she feels represents his/her perception of his/her current state. The VAS score is determined by measuring in millimetres from the left hand end of the line to the point indicated by the participant.

9.8 Assessment of the Compression Bandaging

The following questions will be asked to assess the compression bandaging during the Run-in and Treatment Phase visits:

1. Whether the bandage was in place at each visit (Yes/No)
2. If the bandage was not in place, the date it was removed and the reason for removal (slippage, strikethrough or other)
3. If the bandage is in place but needs to be changed at an unscheduled visit, the reason for removal/change must be recorded from the following:
 - a. Maximum wear time

- b. Participant withdrawn
- c. AE
- d. Slippage
- e. Dressing change needed with details of dressing in question
- f. Soiled
- g. Participant request
- h. Other

9.9 Study Ulcer Leg and Ulcer Assessments

The following assessments of the study ulcer/ study ulcer leg will be conducted as specified below.

9.9.1 Venous Clinical Severity Score

The Venous Clinical Severity Score (25) will be obtained only at the RV1, RV5 visit and at the last study visit. See Appendix 3 for details regarding scoring.

9.9.2 Leg Oedema Assessment (Study ulcer leg only)

The study ulcer leg oedema will be assessed during the study visits using a modification of the Guelph General Hospital Congestive Heart Failure Pathway leg oedema scale (26).

Leg Oedema Scale
• No
• 1+ : Mild pitting, slight indentation, no perceptible swelling of the leg
• 2+ : Moderate pitting, indentation subsides rapidly
• 3+ : Deep pitting, indentation remains for a short time, leg looks swollen
• 4+ : Very deep pitting, indentation lasts a long time, leg is very swollen

9.9.3 Study Ulcer Margin Assessment (Pre-debridement)

The study ulcer margins will be assessed during study treatment visits and the presence/absence of the following features will be recorded (27):

- Granulating
- Epithelialising
- Sloping
- Rolled
- Punched out

- Everted
- Purple
- Undermining
- Sinus
- Inflamed

9.9.4 Study Ulcer Bed Appearance (Pre-debridement)

The study ulcer bed appearance will be assessed during study treatment visits and the following features will be recorded:

- Percentage granulation tissue
- Quality of granulation tissue
- Percentage non-viable tissue

9.9.5 Study Ulcer Exudate Assessment

The Investigator will determine the amount and type, if any, of study ulcer exudate. In determining the amount of study ulcer exudate the Investigator should take into account the amount of exudate absorbed into the study ulcer dressing. The following categories will be used to quantify the amount of study ulcer exudate:

- No exudate
- Minimal amount
- Moderate amount
- Heavy/large/copious amounts

9.9.6 Study Ulcer Surrounding Skin Assessment

The study ulcer surrounding tissue within 4 cm of the ulcer edge will be assessed and presence/absence of the following features will be recorded:

- Tissue paper skin
- Peri-ulcer oedema
- Eczema
- Maceration
- Dry/scaly skin
- Erythema
- Healthy skin
- Inflammation
- Pustules
- Rash
- Skin abnormalities such as scarring

9.9.7 Study Ulcer Infection Assessment

The presence/absence of infection at the study ulcer site will be documented at each study visit. All participants who show evidence of an ulcer infection during the Treatment Phase must have the infection reported on an AE CRF. Any AEs during Run-in Phase are recorded in the participant's medical history.

The determination of presence/absence of ulcer infection will be made by the Investigator. The participant should be treated with topical antimicrobials or oral antibiotics in accordance with local best practice. SC, or SC plus geko™ treatment will continue at Investigator's discretion during the Treatment Phase. Antibiotic interventions will be recorded on the Concomitant Medications Form and the event will be categorised as an AE, serious if it meets the definition of that category.

All participants will be instructed to contact the Investigator if signs or symptoms of infection develop prior to their next scheduled visit.

During an episode of infection, any modification of compression treatment is at the discretion of the Investigator and will be recorded in the CRF.

9.9.8 Investigator Assessment of Study Ulcer Healing

“Healing” is defined as 100% re-epithelialised without drainage determined by the PI or designee as confirmed at the Healing Confirmation visit (HCV). This means that in order to be considered as “healed”, the study ulcer will need to remain closed without drainage for a minimum of 7 days from the date when it is first determined to be 100% re-epithelialised without drainage.

At each TV visit and at the HCV if scheduled, the PI or designee will assess the wound by answering the following questions:

- Is the study ulcer 100% re-epithelialised?
- Is there any drainage present?

When the Questions are asked at a TV visit, if question 1 is answered “yes” and question 2 is answered “no”, the patient is scheduled for a Healing Confirmation Visit (HCV) in a minimum of 7 days. During the HCV questions 1 and 2 above are repeated. Question 1 must be answered “yes” and Question 2 must be answered “no” at the HCV for the study ulcer to be considered healed.

“If Question 1 is answered “yes” and Question 2 is answered “no”, the date of healing will be the date the 100% re-epithelialisation without drainage was first determined by the PI or designee.

9.9.9 Study Ulcer Images

The study ulcer will be digitally photographed according to the schedules in this protocol using the Aranz SilhouetteStar™, a digital camera which is part of the Silhouette™ system.

SilhouetteStar™ is a portable, non-contact device for imaging and measuring ulcers. This system will be used to measure the study ulcer area and to assess the study ulcer appearance.

Run-in Phase and Treatment Phase images of the study ulcer will be taken at each weekly visit, as well as at the HCV, if scheduled, will be used to measure and document ulcer size and healing status.

If debridement is performed, both pre and post-debridement images will be taken. The pre-debridement measurement will serve as the basis for all wound area related endpoints in this study.

All SilhouetteStar™ users must have training in the used system prior to undertaking any imaging and/or measurements for this study. A separate imaging and measurement manual with more detail about SilhouetteStar™ will be provided in the Operations Manual for the study.

If the index ulcer during the course of healing splits into a number of smaller wounds, the area's of the resulting wounds will be combined and used for analysis.

At end of study all images will be sent to an independent blinded wound expert for wound area measurements. The wound area measurements will be used for all PAR related analysis.

9.10 Recording of Device Usage

The participants randomised to the geko™ study group will be provided with a participant diary for the purpose to record the daily geko™ device usage.

10 Statistical Analysis

10.1 General Statistical Considerations

This section presents general information concerning the statistical analyses which will be performed in this study, including for example, information about sample size, interim analysis, randomisation, treatment groups, endpoints, and the analysis methods and statistical tests to be performed. Detailed information on these and other related matters will be provided in the study Statistical Analysis Plan (SAP), as a separate document.

10.2 Sample Size Determination and Rationale

The sample size calculation is based on pilot data pooled from two sources (The Canadian Bandaging Trial (28), and case series) and gives an estimate of effect size (delta/standard deviation) ranging from 0.80 to 1.1. In this design, each group is internally controlled by a four-week baseline, allowing pair-wise intra-group comparison, and normalised inter-group comparison. Assuming the more conservative figure for effect size, and assuming 50% effect size for the reduced dosage group, n=35 per group yields 90% power to establish an effect for geko™ at the lower dosage.

Because of the short study duration, the discontinuation rate is predicted to be about at most 20%. To accommodate the potential discontinuations, the trial proposes to randomise 126 subjects (42 per treatment group).

10.3 Randomisation

This is a multi-centre randomised clinical study. Participants will be allocated to treatment groups using Adaptive Covariate Randomisation using an on-line randomisation tool (29).

The randomisation will be applied centrally across the sites.

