10.7 Description of Study Endpoints

10.7.1 Primary Efficacy Endpoint

The primary efficacy endpoint for the study is LHR from TV1 to EOT as compared with LHR from RV1 to TV1. LHRs will be measured by a blinded wound expert using digital images at RV1, TV1, EOT, and at HCV if scheduled.

Each participant will be used as his/her own control, i.e. a participant's healing trajectory before commencement of treatment will be compared to his/her healing trajectory after introduction of treatment.

Since significant non-homogeneity may be expected in VLU participants and their respective healing trajectories, a pre-treatment run-in phase will be used to allow each participant to be used as his/her own control, i.e. a participant's healing trajectory before introduction of treatment will be compared to his/her healing trajectory after introduction of treatment. This allows an intra-group pair-wise comparison to evaluate the efficacy of each treatment regimen.

Additionally, for each participant, it enables generation of a treatment healing rate normalised relative to an initial healing rate. Inter-group (albeit un-paired) comparisons based on this normalised value are likely to be more sensitive than comparison of raw healing rates.

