10.12.1 Efficacy Analyses

Primary Endpoint: The primary efficacy endpoint is linear healing rate (LHR) from TV1 to EOT as compared with LHR from RV1 to TV1. LHRs will be measured by a blinded wound expert using digital images at RV1, TV1, and EOT.

Within treatment groups, treatment phase will be compared to run-in phase by paired non-parametric test (Wilcoxon signed rank). Effects will be compared between groups using non-paired non-parametric tests (Mann-Whitney).

Secondary Endpoints:

Weekly LHR shall be compared as above.

EOT healing status between groups shall be compared by Mann-Whitney U test on the PWAT scores. Weekly LHR can be tested using the same method (and same wording) as final LHR. Incidence of healing shall be compared between groups using Fisher's exact test.

Intra-group pain reduction measured on a visual analogue scale (VAS) will be analysed using paired t-test.

Inter group differences in time to clinically significant reduction in VAS shall be tested using Mann-Whitney u-test.

Intra-group changes to both Quality of Life (QoL) instruments in the study (CWIS and EQ-5D-5L) shall be tested using Wilcoxon signed rank test.

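### Allocation is covariate-adaptive, but every named between-arm test ignores the allocation factors; to the extent those factors predict outcome, the tests are conservative and lose power

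*Combined protocol and SAP*

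**What the plan says.** Allocation (protocol 10.3, repeated in the synopsis): "Participants will be allocated to treatment groups using Adaptive Covariate Randomisation using an on-line randomisation tool (29". The section adds that "The randomisation will be applied centrally across the sites". No covariate, weight or random element is given, and the text does not say whether site is a balancing factor.

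Between-arm tests (10.12.1):
- LHR, and weekly LHR by the same method: "Effects will be compared between groups using non-paired non-parametric tests (Mann-Whitney".
- PWAT: "EOT healing status between groups shall be compared by Mann-Whitney U test on the PWAT scores".
- Healing: "Incidence of healing shall be compared between groups using Fisher's exact test".
- Pain: "Inter group differences in time to clinically significant reduction in VAS shall be tested using Mann-Whitney u-test".

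None of these carries a covariate, a stratum or a re-randomisation step. ANCOVA is in the abbreviations list, but no analysis uses it.

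The only baseline adjustment described is in 10.7.1, where a participant's treatment-phase healing rate is normalised to the run-in rate: "Inter-group (albeit un-paired) comparisons based on this normalised value are likely to be more sensitive than comparison of raw healing rates". Within arms, 10.12.1 specifies: "Within treatment groups, treatment phase will be compared to run-in phase by paired non-parametric test (Wilcoxon signed rank".

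Sections 10.1 and 10.12 leave detailed methodology to a separate SAP, to be approved before database lock. It is not part of the supplied text.

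**The concern.** Covariate-adaptive allocation makes the arms more alike on the chosen factors than chance would. If those factors predict outcome, the arm difference varies less from trial to trial than under simple randomisation. Mann-Whitney and Fisher's test take their reference distribution from simple randomisation, so they overstate that variability. Their real level then falls below the nominal one, and the precision that balancing was meant to buy is not used.

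The objective is geko 12 h plus standard care against standard care alone. Only the between-arm tests draw on the randomisation to answer it, and no power is stated for any of them.

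**Working it through.** **1. The plan's own figure.** Section 10.5.2 gives a mean change of 0.58 mm/week, SD 0.97, 80% power and two-sided 0.05, for geko 12 h run-in versus treatment, and states 25 subjects. Normal approximation: ((1.960 + 0.842) × 0.97 / 0.58)² = 21.95, so 22. The exact paired t calculation gives 24 (power 80.1%; 81.8% at 25), and 24 / 0.955 for Wilcoxon efficiency gives 25.1. The figure reproduces. It is a within-arm test, so the allocation method has no bearing on it.

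**2. The between-arm starting point.** The plan gives no between-arm difference. Assume the same 0.58, SD 0.97 in both arms (0.58 / 0.97 = 0.60 SD) and 1:1 allocation of the 60 participants in 3.1.1. Power = Φ(0.58 / (0.97 × √(2/n)) − 1.96):
- n = 30 per arm: Φ(2.316 − 1.96) = 64%.
- n = 24 per arm (the 20% discontinuation in 10.2): Φ(2.071 − 1.96) = 54%.
- 80% power needs 2 × 21.95 = 43.9, so 44 per arm.

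**3. Why the level falls.** Let R² be the share of outcome variance that the allocation factors explain. Under near-perfect balance, the null SD of the unadjusted statistic is about √(1 − R²) instead of 1, so the real two-sided level is about 2Φ(−1.96 / √(1 − R²)). At R² = 0.3 that is 2Φ(−2.34) = 1.9%.

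**4. Simulation.** Assumptions: N = 60, minimisation with a biased coin of 0.85, normal outcomes. Set A has three binary factors and a difference of 0.58 with SD 0.97 (4,000 null and 2,500 alternative runs per cell). Set B has two binary factors and one three-level factor, and a difference of 0.6 SD (4,000 runs per cell). MW is Mann-Whitney and RA is rank ANCOVA on the allocation factors.

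| R² | Level by formula | Level, MW / RA (A) | Power, MW / RA (A) | Power, MW / RA (B) |
|---|---|---|---|---|
| 0 | 5.0% | 4.2 / 4.6% | 61 / 61% | 60 / 61% |
| 0.1 | 3.9% | 4.0 / 5.1% | 60 / 64% | 61 / 65% |
| 0.2 | 2.8% | 3.0 / 4.9% | 61 / 69% | 60 / 68% |
| 0.3 | 1.9% | 2.4 / 5.3% | 59 / 74% | 60 / 75% |
| 0.5 | 0.6% | 0.9 / 4.7% | 62 / 86% | not run |

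Monte Carlo error is about 1 point for power (√(0.6 × 0.4 / 2500)) and 0.3 points for level (√(0.05 × 0.95 / 4000)). With 48 evaluable participants, set A gives power of 51 / 51%, 51 / 55%, 51 / 60%, 49 / 63% and 48 / 78% over the same R² values.

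**5. Control.** Under simple randomisation at R² = 0.3, Mann-Whitney has a level of 5.5%, with power of 58% against 71% adjusted. The low level is therefore specific to adaptive allocation. Most of the power gap is the ordinary gain from adjusting for a prognostic factor.

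**6. Many-level site factor.** Assume 48 evaluable participants, a 10-level site factor plus two binary factors, and a 0.6 SD difference (2,000 runs). Power, Mann-Whitney against rank ANCOVA, is 52 / 48% at R² = 0, 50 / 50% at 0.1 and 50 / 54% at 0.2.

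**7. Healing.** With 10% healing per arm (assumed) and no prognostic factor, Fisher's test already has a level of about 2.0%, from discreteness alone. With a strong assumed factor, stratifying raised power from about 54% to 59%.

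**The case against.** The strongest reply is that the harm is conditional and its condition is not in the documents. No allocation factor is named, and at R² = 0 nothing is lost. This stands: a reader might infer that the real level of every between-arm test is known to differ from 5%, and the documents do not support that.

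For LHR, the comparison is built on each participant's change from his or her own run-in. Factors that act alike in both phases largely drop out, so R² values of 0.2 to 0.3 may be too high for that endpoint. This also stands. The protection does not extend to PWAT, healing or time to pain reduction, so the effect need not be equal across endpoints. For healing, part of the conservatism belongs to Fisher's test itself.

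Adjustment is not always free. With a many-level site factor it can cost more than it returns when prognostic value is low. This stands and shapes the fix.

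The pending SAP could add adjustment. That answers the point only in part: 10.1 presents section 10 as covering the methods and tests to be performed, and 10.12.1 names unadjusted ones. A SAP not yet approved makes the change easy, whereas adjustment chosen after seeing the data would be open to challenge.

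**Conclusion.** The mismatch between 10.3 and 10.12.1 is established, and the direction is clear: to the extent the allocation factors predict outcome, between-arm p-values are too large on average and power is lost. The size is not established. With three few-level factors, N = 60 and a 0.6 SD difference, the loss is 0 points at R² = 0, about 4 at 0.1, 8 to 9 at 0.2 and 14 to 15 at 0.3. It is probably smaller for LHR. These figures rest on assumed factors, biased coin, 1:1 ratio, normal outcomes and a between-arm difference borrowed from the within-arm figure.

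Two stronger readings are tempting and unsupported. One is that the stated 80% power is eroded; it belongs to the paired test within geko 12 h, which allocation does not affect. The other is that false positives are inflated; the error runs the other way. It still matters, because on the same inputs the between-arm comparison starts at only about 64% power, or 54% after 20% discontinuation.

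**What to change.** - **10.3:** name the allocation covariates and their levels, and say whether site is one of them.
- **10.12.1 and the SAP, before database lock:** pre-specify between-arm analyses that carry those covariates. Use rank ANCOVA, or van Elteren if the factors are few, for LHR change and PWAT, and likewise for weekly LHR and time to pain reduction if they remain rank comparisons. For healing, use an exact test stratified by the main allocation factor.
- **Sensitivity:** keep the unadjusted Mann-Whitney and Fisher tests in this role, described as conservative to the extent the factors are prognostic.
- **If site is a many-level factor:** pool small sites by a rule set in advance, or use a re-randomisation test. Carrying ten levels costs about 3 to 4 points of power when the factors are not prognostic. A re-randomisation test must replay the allocation as it ran, including the period when the 6 h arm was open.

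The cost is wording, with no new data or participants, since the allocation tool must already hold the covariates. Adjustment uses a few degrees of freedom; with few factors, simulated power at R² = 0 was essentially unchanged (61% against 61%, and 60% against 61%).
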